6 STUDY INTERVENTION

6.1 STUDY INTERVENTION

6.1.1 STUDY INTERVENTION

The basic **delivery elements** of the EPIC intervention are as follows:

- **Initiation across COPD severity stages:** The intervention is administered to patients across COPD severity stages (moderate to very-severe COPD)
- **Nurse coach-led:** The intervention is led by trained nurse coaches with weekly and as needed supervision by the PI and specialist palliative care clinicians.
- **Charting Your Course (CYC) Curriculum: *An Intervention for Patients with COPD and their Caregivers*:** The CYC curriculum is a reproducible and scalable telephone-based coaching curriculum informed by prior ENABLE trials with telephone scripts and patient and caregiver guidebooks.
 - **Patients complete six sessions, and caregivers complete four weekly sessions, followed by monthly check-in calls and homework assignments.**
 - Sessions 1-3 are founded on **MacMillan's COPE** (Creativity, Optimism, Problem-solving, Expert information) model. Sessions 4-6 are guided by the **OUTLOOK model** for life review and leaving a legacy.
 - Palliative nurse coaches begin each CYC session with distress screening and barrier identification.
- **Telephone coaching sessions:** These sessions cover specific topics every 1 to 2 weeks. Each last 20 minutes/session [or up to 1 hour if needed] and are followed by monthly telephone follow-up. Coaches engage participants in learning how to care for themselves and teach caregivers how to be active partners in their loved one's care.
- **Distress screening and individualized problem solving support:** Each encounter begins with distress screening (based on the NCCN distress thermometer) to identify potential problems that may need assistance with and to help customize core sessions.
- **EPIC Toolkit:** Participants receive an EPIC toolkit (hereafter "Toolkit"), a packet that contains educational information pertaining to the coaching sessions. The Toolkit also serves as a tool to organize intervention materials and as a resource guide for the participant. The Toolkit is hand delivered at the first session or mailed prior to initiation of core sessions.

6.1.2 SUMMARY OF PROTOCOL

Training of Study Team Members

The intervention requires two nurse coaches who are hired and trained by the PI and co-investigator, [name]. Advanced training specific to EPIC consists of independent readings, review of all intervention materials and the protocol, in-depth discussions on COPD and its management, and thorough review of the protocol. The PI will chair weekly nurse coach meetings to review progress and intervention receipt.

Enrollment Procedures.

All agreeable and eligible patient participants who consent to participate in the study complete an intake form that includes demographic data (all participants), clinical data (patients only), and symptom surveys (patients and caregivers). We are measuring Life-Space mobility, quality of life, caregiver burden, functional status, mood symptoms, loneliness, and cognitive impairment. If time allows for participants, baseline surveys will be completed immediately after consent. If time does not permit in the patient's schedule, the intake surveys will be completed by telephone at a mutually-agreed upon time. Agreeable and eligible caregivers who consent to participate in the study will also be provided a short intake form of their demographic and background information as well as intake symptom surveys. If the time does not permit in the caregiver's schedule, the intake surveys will be completed by telephone at a mutually agreed upon time.

Summary of Randomization Procedures.

Randomization will take place after the informed consent and intake are obtained from both the patient and the caregiver. We will randomize 30 patient-caregiver dyads in a 1:1 fashion to the study arms: 1) EPIC + usual care (n=15 dyads); and 2) usual care alone (n=15 dyads). A randomization table will be generated to allocate all 30 dyads to the study arms. Randomization procedures will be supervised by the biostatistician, [name] (Co-I and trial statistician) at UAB. The randomization scheme will be executed using an Excel randomization table and recorded in REDCap. The study coordinator will complete the randomization procedure and record study group in REDCap. The study coordinator will inform the usual group participants of their group assignment and will also alert the interventionists to initiate intervention activities with the intervention group participants.

6.1.3 SUMMARY OF TRIAL PROCEDURES

Control Arm

The control arm of the study will be usual care for COPD in pulmonary clinic (**Table 1**) which includes symptom management, inhalers, advanced COPD therapies as needed, illness education, informal tobacco cessation counseling, supplemental oxygen testing, and referral to cardiopulmonary rehabilitation and other services as appropriate per the clinician.

Table 1. Control Arm Procedures and Timeline (Usual Care)					
Study Week	Type of Session	Investigator	Participant	Estimated Participant Time (minutes)	Description
1	In-person/ Phone	Coordinator	Patient + Caregiver	60	Study introduction, informed consent, intake surveys
2-24	N/a	N/a	Patient + Caregiver	N/a	Usual COPD care
12	Phone	Data Collector	Patient + Caregiver	60	Midpoint surveys
24	Phone	Data Collector	Patient + Caregiver	60	Exit surveys
24	Phone	Coordinator	Patient + Caregiver	30	Post-intervention acceptability survey Post-intervention feedback interview

Intervention Arm

Dyads randomized to the intervention arm will receive EPIC along with usual care (**Table 2**). EPIC includes weekly, telephone-based palliative care nurse coaching aided by the manualized curriculum, *“Charting Your Course (CYC): An Intervention for Patients with COPD and their Caregivers”*. This is followed by brief telephone follow-up calls monthly until study completion. Patient participants are also scheduled for a visit with the Supportive Care Clinic at The Kirklin Clinic, where trained clinicians complete a comprehensive palliative care assessment, virtually if preferred. Current intervention materials for EPIC and nurse coach CYC phone scripts are being edited and refined. Final copies of all intervention materials and phone scripts will be submitted as an amendment at a later date.

Table 2. Intervention Arm Procedures and Timeline (EPIC + Usual Care)					
Study Week	Type of Session	Investigator	Participant	Estimated Participant Time (minutes)	Description
1	In-person/ Phone	Coordinator	Patient + Caregiver	60	Study introduction; consent; intake surveys
2-12	In-person/ Virtual	N/A	Patient + Caregiver	60	Supportive Care Clinic visit; comprehensive palliative care assessment
3	Phone	Nurse coach	Patient + Caregiver	45	CYC Session 1: Problem solving
4	Phone	Nurse coach	Patient +	45	CYC Session 2: Self-care management

			Caregiver		
5	Phone	Nurse coach	Patient + Caregiver	45	CYC Session 3: Assessing, prioritizing, and managing symptoms
6	Phone	Nurse coach	Patient + Caregiver	45	CYC Session 4: Communication skills, decision-making, and advance care planning.
7	Phone	Nurse coach	Patient only	30	CYC Session 5: Life review, supportive counseling
8	Phone	Nurse coach	Patient only	30	CYC Session 6: Leaving a legacy
12	In-person or Phone	Data Collector	Patient + Caregiver	60	Midpoint surveys
12-24	Phone	Nurse coach	Patient + Caregiver	20	Monthly telephone check-in call
24	In-person or Phone	Data Collector	Patient + Caregiver	60	Exit surveys
24	Phone	Coordinator	Patient + Caregiver	30	Post-intervention acceptability survey + phone feedback interview
24	Phone	Coordinator	Patient + Caregiver	30	Post-supportive care clinic visit survey

CYC sessions refer to the chapters in the patient and caregiver guidebooks. The coordinator and nurse coaches record completion of the sessions in REDCap. Patient participants complete CYC Sessions 1-6, while caregiver participants complete CYC Sessions 1-4.

Materials

Participants randomized to the intervention arm will be mailed a study packet consisting of the following: 1) EPIC introductory materials including an introduction of the study team; and 2) EPIC toolkit for patients and caregivers consisting of CYC materials, blank activities sheets, resources, and a blank Advance Directive.

Charting Your Course Curriculum

The project coordinator will notify the nurse coaches of participant enrollment and randomization to the intervention arm to schedule the CYC sessions at home by telephone. Patients randomized to the intervention arm will receive telephone calls by a trained nurse coach guided by telephone scripts. Caregivers will receive separate telephone calls by a different nurse coach following the same procedures. In the first telephone call, the nurse coach will introduce themselves and will describe the overall EPIC intervention. Patient participants will then begin 6 weekly intervention telephone sessions with the nurse coach. The nurse coach will call the patient at home for each session at a time that is convenient for the patient. The sessions cover the materials found in the CYC guidebook and follow telephone scripts. All CYC sessions will be audio-recorded as conducted in previous trials for fidelity monitoring. The PI will conduct fidelity monitoring on at least 50% of all audio-recordings as described below.

Figure. EPIC CYC Sessions for Patients and Caregivers							
Sessions	1	2	3	4	5	6	Follow-Up
Patient	COPE, Problem Solving	Self-care	Symptom Management	Communication, Support, Decision-Making	Life Review, Accomplishments	Forgiveness, Regrets, Creating a Legacy	Monthly Follow-Up (Telephone)
Caregiver	COPE, Problem Solving, Role	Self-care	Being a Partner in Symptom Management	Communication, Support, Decision-Making	Monthly Follow-Up (Telephone)		
Activities	Medications and Symptom List, Activity Log, Communicating with Providers Checklist, Ottawa Personal Decision Guide, and Advance Directive						

Each telephone session with the nurse coach begins by asking if the time is convenient for the participant, a reminder that the calls are audio-recorded for fidelity monitoring and quality assurance, and an assessment of the patient participant's level of distress using the National Comprehensive Cancer Network's Distress Thermometer included in the guidebooks. The nurse coach uses the telephone script to guide conversation with the participant. The nurse coach will call back monthly after completing the last CYC session to review any needs of the patient participant per the nurse coach telephone script and to assess maintenance of practices. Caregiver participants will separately complete 4 intervention telephone sessions using their own guidebook. Phone calls will be scheduled at a day and time that is convenient for the caregiver participant, and the nurse coach.

Post-intervention Interviews

Post-intervention interviews of participants will be conducted by the trained project coordinator using an interview guide to seek participant feedback and experiences of the intervention for those randomized to intervention and the overall project for all participants. The study coordinator will conduct the interviews by telephone. He or she will ask participants if this is a good time to talk and will remind the participant that the interviews are audio recorded and transcribed. The study coordinator will allow the participant to skip any questions if needed. The electronic audio file will be stored on a password-protected computer by the study coordinator and uploaded to the secure website of Landmark Associates for verbatim transcription. The PI will review every 5 transcripts for fidelity monitoring and to refine the interview. The transcription text will be coded with the participant's study identification number and reviewed by the PI to remove any protected health information from the text, including names, places, and affiliations. The digital file of the audio recording will be deleted after review of the transcript.

6.2 FIDELITY MONITORING

6.2.1 INTERVENTIONIST TRAINING AND TRACKING

Training. We have a structured orientation checklist and treatment manual that will be used to train interventionists. Drs. [name] (PI) and [name] (Co-I) will train two nurse coaches (one for each participant type) to deliver the intervention. Nurses are well suited to learn EPIC as it builds upon their expertise in therapeutic relationship building, distress screening, and resource referral. The training program is approximately 70 hours in length and is modeled on procedures developed by our study team over the course of several clinical trials of behavioral interventions and our current pilot trial. The training consists of independent readings, interactive online modules, videos including demonstration of coaching techniques (e.g., active listening, single and double-sided reflections), review of all study protocols and procedures, provision of the treatment manual, and role play of six training cases.

Supervision. Throughout the study, interventionists will have weekly supervisory meetings with Drs. [name] and [name] to review calls and sessions with all active intervention-group participants. In addition, nurse coaches will have 24-7 access to Drs. [name] and [name] for any participant issues that arise.

Fidelity. Consistent with our prior trial procedures, all palliative care coach phone sessions will be audio recorded, and a random sample of at least 50% of these audio recordings will be scored quarterly using a checklist to ensure that treatment is being administered reliably over time and across palliative care coach. For each scored session, feedback will be reviewed with the palliative care coach in order to maximize performance and expertise. A palliative care coach who exhibits a pattern of non-adherence on three consecutive ratings will be required to receive additional training and supervision. The PI and study coordinator will also randomly sample 50% of the geriatric-palliative care assessments from the supportive care clinic visits at least quarterly to ensure the elements of the assessment were completed.

6.3 MEASURES TO MINIMIZE BIAS: RANDOMIZATION AND BLINDING

The randomization scheme will be executed via REDCap, a clinical trials management software program used for randomization and data tracking. Participants will be randomly assigned to group in a 1:1 fashion using a computer-generated program overseen by [name] (Co-I and trial statistician) at UAB. The study coordinator will be alerted to the assignment in REDCap. The study coordinator will inform the usual group participants of their group assignment and will also alert the interventionist to initiate intervention activities with the intervention group participants. Data collectors will remain blind to group assignment, and participants will be instructed not to discuss their assignment with the UAB data collector facilitating questionnaire completion over the telephone.

6.4 STUDY INTERVENTION/EXPERIMENTAL MANIPULATION ADHERENCE

Four strategies (consistent with NIH and TIDieR guidelines) will ensure intervention fidelity: 1) Interventionist training will be standardized and overseen by Drs. [name] and [name]; 2) Nurse coaches will follow study-team developed intervention scripts for each of the core sessions and monthly follow-up; 3) For each intervention contact, charting templates will be used by interventionists to further ensure that essential topics are addressed; and, 4) During the study, 50% of nurse coach sessions will be

randomly selected for treatment fidelity monitoring by [name] using a fidelity checklist developed in our pilot trial. Of the sessions chosen for fidelity checks, audio-recorded sessions of the CYC sessions will be randomly selected for ratings. If ratings are below 80% adherence, supervision will focus on necessary techniques to improve the score.

6.5 CONCOMITANT THERAPY

6.5.1 RESCUE THERAPY

N/A

7 INTERVENTION DISCONTINUATION AND PARTICIPANT DISCONTINUATION/WITHDRAWAL

7.1 DISCONTINUATION OF STUDY INTERVENTION

Participants may withdraw or voluntarily stop their intervention sessions at any time. The reason(s) for discontinuing the intervention will be documented (e.g., intervention too burdensome, repeated missed intervention sessions, too busy, patient too ill, etc.), and the participant will be invited to continue with data collection at 12 and 24 weeks and beyond.

7.2 PARTICIPANT DISCONTINUATION/WITHDRAWAL FROM THE STUDY

Participants are free to withdraw from participation in the study at any time upon request. Reasons for participant discontinuation or withdrawal from the study will be recorded. The PI may discontinue a participant from the study for the following reasons:

- Significant study intervention non-adherence
- Lost-to-follow up; unable to contact participant (see **Section 7.3, Lost to Follow-Up**)
- Any event or medical condition or situation occurs such that continued collection of follow-up data would not be in the best interest of the participant

7.3 LOST TO FOLLOW-UP

A participant will be considered lost to follow-up if he or she fails to show up for **3 scheduled appointments** with the nurse coach, and study staff are unable to contact the participant after **at least 3 attempts**. All lost-to-follow up decisions will be made by the PI as special circumstances may warrant additional study contact attempts. The following actions are taken if a participant fails to complete intervention sessions or data collection time points:

- Research staff will attempt to contact the participant, reschedule the missed component (eg. CYC session), counsel the participant on the importance of adhering to the assigned schedule and ascertain if the participant wishes to and/or should continue in the study
- Before a participant is deemed lost to follow-up, the research team will make every effort to regain contact with the participant. Contact attempts will be documented in the study's tracking system.
- Should the participant continue to be unreachable, he or she will be considered to have withdrawn from the study with a primary reason of lost to follow-up. Withdrawal letters are found in the Appendices section.

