3 AIMS AND OUTCOMES

TRIAL OUTCOMES - SUMMATIVE EVALUATION	
RE-AIM Implementation Framework (Aims 1 & 2)	
Reach Trial feasibility	Rates of screening, enrollment, retention, reasons for exclusion and refusals, randomization, and attrition.
Adoption Intervention feasibility	Mean rates of completion of core EPIC components out of possible 10 for patients and 8 for caregivers. Feasibility: Overall average completion of ≥8 sessions for patients ≥6 sessions for caregivers .
Acceptability	Quantitative (Patients/Caregivers): Post-intervention survey on intervention acceptability. Acceptability: Overall average score ≥8 of 10. Qualitative (Patients/Caregivers): Post-intervention semi-structured, in-depth interviews by telephone to explore acceptability, barriers, facilitators, and survey burden.
Implementation Intervention fidelity	A random sample of 50% of palliative nurse coach sessions will be reviewed monthly using a rigorous fidelity checklist. Palliative nurse coaches who exhibit a pattern of non-adherence on three consecutive ratings will receive additional supervision and training.
Survey completion	Quantitative: Survey completion rates. Feasibility: ≥80% of participants complete all surveys
Define usual care arm	Review electronic medical record to capture elements of “usual COPD care”.
Maintenance	Nurse coaches check in monthly to reinforce EPIC. Interviews explore barriers to maintenance.
“Effectiveness” (Exploratory Aim; Secondary Outcomes at Baseline, 12 weeks, and 24 weeks, where indicated)	
Life-Space Mobility (Target Secondary Outcome; R01 outcome)	UAB Life Space Assessment (LSA) (Patients/Caregivers): 15-item measure of community mobility; frequency, distance, and independence of movement in the 4 weeks prior to administration; LSA<60 (restricted Life-Space mobility) Lower scores → more restricted; MCID=5 points ($\alpha=0.80$).
Quality of Life	Chronic Respiratory Questionnaire (Patients): 20-item measure of quality of life in COPD; domains of dyspnea , fatigue , emotional function , and mastery . Higher scores → better. MCID=0.5 ($\alpha=0.70$) PROMIS Global Health 10 (Patients/Caregivers): 10-item measure; physical and mental health domains; 9 questions rated on a 5-point Likert-scale, and 10th question rates pain on a scale of 0 to 10. Raw scores converted to standardized t-scores ranging from 0 to 100, with lower scores → worse QOL.

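### Section 7.3 has two inconsistent routes to lost to follow-up, one open only to the EPIC arm and before any survey is due, so retention can be counted differently by arm

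*Combined protocol and SAP*

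**What the plan says.** Section 7.3 opens with a definition in two limbs: "A participant will be considered lost to follow-up if he or she fails to show up for" three scheduled appointments "with the nurse coach, and study staff are unable to contact the participant after" at least three attempts. Both limbs are required. The investigator keeps discretion: "All lost-to-follow up decisions will be made by the PI as special circumstances may warrant additional study contact attempts".

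The same section then gives a wider instruction: "The following actions are taken if a participant fails to complete intervention sessions or data collection time points". Its last bullet says that if the participant stays unreachable, "he or she will be considered to have withdrawn from the study with a primary reason of lost to follow-up". The coach condition is not repeated there, and no number of misses is given.

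On the control arm, section 6.1.3 says "The control arm of the study will be usual care for COPD in pulmonary clinic". Table 1 lists no coach session, only surveys at weeks 12 and 24 and a coordinator call at week 24. In section 6.3 the coordinator tells usual-care participants their assignment and "will also alert the interventionist to initiate intervention activities with the intervention group participants".

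Section 3 lists the trial-feasibility outcomes under Reach: "Rates of screening, enrollment, retention, reasons for exclusion and refusals, randomization, and attrition". Section 9.1 includes retention in Hypothesis 2, labelled primary. Section 4.4 defines study completion as completing the week-24 questionnaires, in either arm. Section 7.1 names repeated missed sessions as a reason for stopping the intervention, and invites that participant to continue data collection at weeks 12 and 24.

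**The concern.** The only explicit definition of loss depends on a contact that one arm does not have. The wider route reaches both arms, but it starts at a different time in each, because the first thing a control can miss after randomization is the week-12 survey. The arm may therefore decide who is withdrawn, and when, among people who are equally hard to reach.

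Retention is part of a primary hypothesis, and the trial exists partly to supply such figures for a larger study. A retention rate that depends on arm-specific contacts is a poor basis for that. An early withdrawal also forfeits week-12 and week-24 data that might have been obtained.

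**Working it through.** **1. Who can meet each route.** EPIC patients have six coaching sessions plus monthly calls, EPIC caregivers have four plus monthly calls, and controls have none (section 6.1.3, Tables 1 and 2). The opening sentence of 7.3 can thus be met by 0 of the 15 × 2 = 30 control participants. Section 10.1.6 mentions coaches contacting participants about their assigned condition, but 6.1.2 and 6.3 give that task to the coordinator for usual care. At most it is a notification, not a scheduled appointment. The closing bullets can be met in either arm.

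**2. When each route can be met.**
- EPIC, weekly sessions (Table 2): sessions 1 to 3 fall in weeks 3, 4 and 5. Allowing about a week for three contact attempts gives about week 6. That week is my assumption; 7.3 sets no interval.
- EPIC, two-week spacing (allowed by 6.1.1): weeks 3, 5 and 7, so about week 8.
- Survey window (section 8.1): 14 business days is 14 × 7/5 = 19.6, about 20 calendar days. It opens at 12 − 20/7 = week 9.1 and closes at 12 + 20/7 = week 14.9. If the 14 days are calendar days, as another phrase in 8.1 could be read, it opens at week 10.
- Control: nothing can be missed before about week 9.1, and failure to complete the week-12 survey is settled only at about week 14.9.
- Section 8.1 lets data collectors start calling within 14 days of the window, possibly from 9.1 − 2 = week 7.1. At two-week spacing that could overlap with the coaching misses, but data collected before the window opens are not evaluable.

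**3. The same spell in each arm.** Take two participants, both unreachable in weeks 3 to 8 and reachable from week 9. The EPIC participant misses three coach appointments, cannot be contacted, and is treated as withdrawn from the study. Section 7.3 provides for no later survey call. The control has nothing scheduled, is called for both surveys, answers, and is a completer under 4.4.

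**4. Scale.** The plan's inflation reproduces: 24/(1 − 0.20) = 30 patients. That is 15 per arm (section 6.1.2), with 12 per arm expected to remain (section 9.2), an allowance of 15 − 12 = 3. One patient classified differently moves an arm's rate by 1/15 = 6.7 points and uses 1/3 of the allowance. Section 4.1 prints 30 patients for each half, which does not fit 30 dyads in total; I use 6.1.2.

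**5. If staff applied the opening sentence alone.** Let *d* be the true loss rate, assumed equal in both arms, and *s* the share of EPIC losses that also have three coach no-shows. The pooled recorded rate is (15·*d*·*s* + 0)/30 = *d*·*s*/2.

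| True loss *d* | *s* = 1 | *s* = 0.5 |
|---|---|---|
| 10% | 5% | 2.5% |
| 20% | 10% | 5% |
| 30% | 15% | 7.5% |

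The documents give only an overall 20%; the other inputs are assumptions. This reading lowers recorded attrition, whereas the early withdrawal in step 3 can raise it in EPIC. The net direction cannot be read from the plan.

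**The case against.** The best defence is that 7.3 should be read as a whole. Its later bullets cover missed data collection, so a control who misses a survey and stays unreachable is recorded as lost. Section 4.4 gives a completion criterion that is the same in both arms, and nothing says that the retention and attrition rates are computed from 7.3. Missed coaching calls alone do not remove anyone: contact must also fail, every effort must be made to regain it, and the investigator decides each case. Section 7.1 already keeps people who merely stop sessions in data collection. The week-6 timing needs consecutive misses and prompt failure of all attempts.

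Most of this stands, and it rules out three stronger readings that a reader might infer.
- That no control can be classed as lost under 7.3. This is true of the opening sentence only.
- That EPIC attrition is over-counted. That would need participants declared lost who would later have answered a survey, and the documents give no figure for this. The two-limb test is also stricter than unreachability alone.
- That the mixed model's missing-at-random assumption fails. Unequal dropout by arm does not in itself violate it in a model that includes arm. Section 9.4.1 plans to adjust for baseline predictors of dropout, and nothing shows that missingness depends on unobserved Life-Space scores.

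The defence does not remove the timing difference, which holds under the wider route too. Nor does it supply a counting rule: 4.4 defines completion, but no section gives the numerator or denominator for retention or attrition.

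**Conclusion.** The concern holds as an inconsistency within 7.3 and a missing counting rule, not as a demonstrated bias. Followed as written, 7.3 can withdraw an unreachable EPIC participant at about weeks 6 to 8, before the survey window opens at about week 9, while a control unreachable over the same weeks is still approached. It also sits badly with 7.1, because repeated missed sessions lead to continued data collection in one section and form half of the test for leaving the study in the other.

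The size is unknown. Each patient affected is worth 6.7 points of an arm of 15. The conclusion assumes that a participant treated as withdrawn from the study receives no later survey calls, which 7.3 implies but does not state, and that the investigator's discretion is not used to delay the decision. It should be corrected because the rates are primary feasibility outcomes.

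**What to change.** Rewrite the definition in 7.3 so that it is the same in both arms:
- Lost to follow-up means that the week-24 survey was not obtained after at least three documented contact attempts within its window. Report week 12 separately on the same basis.
- Record missed coach sessions only as intervention discontinuation under 7.1. Still make the week-12 and week-24 survey calls unless the participant withdraws consent.
- State in section 3 or 9.4.2 that retention and attrition are counted over all randomized participants, by arm and separately for patients and caregivers, consistent with 4.4.

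Replacing the nurse coach with any study contact, while keeping three misses, would not restore symmetry: controls have only two follow-up surveys and one coordinator call. The cost is one paragraph, one field in the tracking log and a few extra survey calls.
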